4.7.7. Supplementary Analyses

In addition to the main analysis, a supplementary analysis will be performed to evaluate whether there is an impact on the primary outcome if HBV DNA TND is observed. For this estimand, the outcome of SVR is defined as observing HBsAg <LLOQ and HBV DNA TND at each analysis window for 24 weeks after the planned end of treatment (EoT). All other elements of this estimand are defined in the same way as in the main analysis.

4.7.8. Exploratory Analyses

4.7.8.1. Efficacy Analyses

Refer to Section 4.4.1 for details.

4.8. Changes to Protocol Defined Analyses

Changes from the originally planned statistical analysis specified in the protocol are detailed in Table 10

Table 10 Changes to Protocol Defined Analyses

Protocol Defined Analysis	SAP Defined Analysis	Rationale for Changes
Section 3 Objectives and Estimands and where applicable throughout	Updated text defining the population for the efficacy objectives align with the definition of intent-to-treat (ITT) population which will be used in efficacy analyses and is defined as all randomized participants.	To align with Study 209668 (B-Clear).
Section 3 Objectives and Estimands and Section 9.4.3.1 Secondary Estimands	Secondary Efficacy Endpoints: moved HBe antibody (anti-HBeAg) levels from a continuous variable to a categorical variable.	Correction.
NA – addition	SAP Section 4.2.5.1: Additional estimand to assess efficacy using a modified definition of SVR	Rationale is based on B-clear study , i.e. there are possible subjects with single lab values that are aberrant in terms of the individual's overall trajectory of response. There is some evidence that the aberrant values have occurred because of an unresolvable error at the site/lab. As the issues cannot be resolved in the data, this analysis will be used to support the primary objective.
Section 9.5 Interim Analysis	Unplanned interim analysis added	Support of internal decisions for platform trial (Study 218309)

5. SAMPLE SIZE DETERMINATION

For the entire study, approximately 100 participants will be enrolled and randomised to achieve approximately 50 participants in each treatment group:

- 24 weeks treatment of GSK3228836 followed by up to 24 weeks treatment of PegIFN
- 12 weeks treatment of GSK3228836 followed by up to 24 weeks treatment of PegIFN

It is assumed that the number of responders follows a Binomial distribution, with a weakly informative prior (Beta (0.5, 0.5)) for the true RR. The precision for a range of RRs with 95% credible intervals are shown in [Table 11](#).

Table 11 95% Credible Interval of Response Rate

Number of Responders	Response Rate	95% Credible Interval*
9	18%	9% - 30%
10	20%	11% - 33%
11	22%	12% - 35%
12	24%	14% - 37%
13	26%	15% - 39%
14	28%	17% - 41%
15	30%	19% - 44%
16	32%	20% - 46%
17	34%	22% - 48%
18	36%	24% - 50%
19	38%	26% - 52%
20	40%	27% - 54%

*95% equal-tailed interval

The historical RR of a combination therapy of NA and PegIFN was 10% with 48 week's treatment [[Ren, 2019](#); [Lee, 2018](#)]. The lower bounds of 95% credible intervals will exclude the RR of 10% if observed RR is greater than or equal to 20% (10 responders out of 50 participants) in an arm.

The posterior probabilities that the true sustained virologic RR is greater than a range of RRs will be calculated from the implied Beta posterior, given the actual number of responders observed.

The operating characteristics based on at least 65% posterior confidence that the true rate exceeds a threshold of interest, are shown in [Table 12](#) for various sample sizes and true

cure rates. The operating characteristics shown are based on a Bayesian inference without consideration of baseline stratification factors.

Table 12 End of study (EoT+24wks) Operating Characteristics by Sample Size

Criterion	Sample Size per Arm	Minimum Number (%) or Responders Required to Meet Criterion	Probability of Meeting Criterion under Various Assumptions			
			True SVR rate = 20%	True SVR rate = 30%	True SVR rate = 35%	True SVR rate = 40%
Probability (true response rate > 20%) > 65%	30	7 (23%)	39%	84%	94%	98%
	40	9 (23%)	41%	89%	97%	99%
	50	12 (24%)	29%	86%	97%	99%
	60	14 (23%)	31%	90%	98%	100%
Probability (true response rate > 30%) > 65%	30	10 (33%)	6%	41%	64%	82%
	40	14 (35%)	2%	30%	56%	79%
	50	17 (34%)	1%	32%	61%	84%
	60	20 (33%)	1%	33%	65%	88%
Probability (true response rate > 40%) > 65%	30	14 (47%)	0%	4%	12%	29%
	40	18 (45%)	0%	3%	12%	31%
	50	22 (44%)	0%	3%	12%	33%
	60	26 (43%)	0%	2%	11%	34%

Based on these operating characteristics, for a true RR of 30%, the proposed sample size of n=50 for each arm has ~86% probability of confirming a true response of at least 20%, and if the true rate is 40%, there is an 84% chance of confirming a true response of at least 30%. There are no plans for sample size re-estimation.

6. SUPPORTING DOCUMENTATION

6.1. Appendix 1: Study Population Analyses

Unless otherwise specified, the study population analyses will be based on the Enrolled Analysis Set. A summary of the number and percentage of participants in each of the participant level analysis set will be provided. Participants excluded from various study populations will be presented in a listing.

Subject enrolment will be presented by country and site ID.

For the interim analysis, a table showing the amount of pending data will be produced for participants with SVR status unknown due to them not having reached the end of off-treatment follow-up (EoT+24wks) at the time of IA. Assessment of pending data should be performed based on occurrence of endpoint analysis window visits.

6.1.1. Participant Disposition

A summary of the number of participants who were screened including number and percentage of screen failures will be provided. In addition, reasons for screen failure will be presented.

A summary of the number and percentage of participants who completed the study as well as those who prematurely withdrew from the study will be provided. Reasons for study discontinuation will be summarized.

A summary of study intervention status will be provided. This display will show the number and percentage of participants who have completed the scheduled study intervention or have discontinued study intervention prematurely, as well as primary reasons for discontinuation of study intervention.

Reasons for screen failures, study withdrawal and study treatment discontinuation will also be presented in listings.

6.1.2. Demographic and Baseline Characteristics

Unless otherwise stated, study population analyses will be based on the Enrolled population.

Study population analyses including analyses of participant's disposition, protocol deviations, demographic and baseline characteristics, prior and concomitant medications, nucleos(t)ide treatment ongoing at randomization, medical history and exposure and treatment compliance will be presented.

Demographic characteristics including sex, age, ethnicity, race, height, weight will be summarized with descriptive statistics.

Baseline characteristics including Body Mass Index (BMI), hypertension, non-steroidal anti-inflammatory drugs (NSAIDs), tenofovir disoproxil fumarate (TDF)/tenofovir alafenamide (TAF) containing medications use, ADV containing medications use, diabetes, eGFR, serum creatinine, urine ACR, platelets, ANC, complement C3, complement C4, complement C5a, complement Bb, CRP, MCP-1, c-ANCA, p-ANCA, and subgroup categories (listed in Section 4.6) will be summarized with descriptive statistics.

Hepatitis B characteristics, as collected on the Hepatitis B Disease Characteristics eCRF, will be summarized using descriptive statistics and will be listed.

6.1.3. Protocol Deviations

Important protocol deviations will be summarized.

Protocol deviations will be tracked by the study team throughout the conduct of the study. These protocol deviations will be reviewed to identify those considered as important as follows:

- Data will be reviewed prior to unblinding and freezing the database to ensure all important deviations (where possible without knowing the study intervention details) are captured and categorised in the protocol deviations dataset.
- This dataset will be the basis for the summaries of important protocol deviations.

6.1.4. Prior and Concomitant Medications

Concomitant medications will be coded using the GSK Drug dictionary. The summary of concomitant medications will be provided by ingredient, i.e., multi-ingredient medications will be summarized for each individual ingredient rather than a combination of ingredients. The summary will be created using ingredient base names, i.e., ingredients with the same base name but different salt will appear under one base name in the summary. Anatomical Therapeutic Chemical (ATC) classifications will not appear in the summary.

A prior medication is defined as any medications that is ended prior to the date of first dose of study drug.

Medications initiated after the first dose of study drug or initiated prior to the first dose of study drug and continued after the first dose of study drug will be counted as concomitant medications. A medication that cannot be determined as prior or concomitant medication due to partially or completely missing start/stop date will be counted as both prior and concomitant medication.

6.1.5. Study Intervention Compliance

A summary of overall compliance for GSK3228836 and PegIFN based on the exposure data will be produced. Overall compliance will be summarized using descriptive statistics as well as the categories <80%, 80%-100%, and >100%.

Compliance will be summarized both in terms of number of injections administered and total dose received during the planned on-treatment period.

Percentage of compliance will be calculated as follows:

$$\text{Study intervention Compliance (\%)} = (\text{Number of actual doses}^{[1]} / \text{Number of planned doses}) * 100$$

$$\text{Study dose Compliance (\%)} = (\text{Total Cumulative Actual Dose}^{[2]} / \text{Total Cumulative Planned Dose}) * 100$$

- 1) GSK3228836 :- The planned number of doses are 26 or 14 for Arm 1 & Arm 2 respectively. The Planned Total Cumulative Dose is calculated by multiplying number of planned doses and dose that is, 300 mg.

$$\text{Planned Total Cumulative Dose} = \text{Number of planned doses} * 300 \text{ mg}$$

- 2) PegIFN: - The planned number of doses are 24 if subject becomes eligible for PegIFN Week 1. If subject becomes eligible after PegIFN Week 1, then follow Protocol table 6 to identify number of planned doses –

Table 6 PegIFN Dosing for Participants becoming Eligible for PegIFN after Week 1

Become Eligible for PegIFN at PegIFN Eligibility Week (Table 5)	PegIFN Dosing (Table 4) should continue until PegIFN Dosing Week
2	23
3	22
4	21
6	19
8	17
10	15
13	12

The Planned Total Cumulative Dose is calculated by multiplying number of planned doses and dose that is, 180 mcg.

$$\text{Planned Total Cumulative Dose} = \text{Number of planned doses} * 180 \text{ mcg}$$

[1] : Subject might receive reduced dose that is smaller than the number of injections. Reduced dose should be still counted as ‘one’ dose for *Number of actual doses* calculations.

[2] : Refer to SAP Section 4.5.1

6.1.6. Additional Analyses Due to the COVID-19 Pandemic

A participant is defined as having a suspected, probable, or confirmed COVID-19 infection during the study if the answer is ‘Confirmed’, ‘Probable’, or ‘Suspected’ to the case diagnosis question from the COVID-19 coronavirus infection assessment eCRF. Numbers of participants with a suspected, probable, or confirmed COVID-19 infection, and of COVID-19 test results will be summarized.

If a high proportion (>5% overall) of participants have a suspected, probable, or confirmed COVID-19 infection, the following data displays will be produced:

- Summary of current (and/or past) medical conditions for participants with COVID-19 adverse events.
- Summary of baseline characteristics for participants with COVID-19 adverse events.

6.2. Appendix 2: Data Derivation Rules

6.2.1. Criteria for Potential Clinical Importance

Grading categories for laboratory tests are determined using the DAIDS grading system Version 2.1 [National Institute of Allergy and Infectious Diseases. Division of AIDS, 2017].

No Laboratory tests values of potential clinical importance (PCI) are defined. Laboratory values outside of normal range will be summarized and listed.

6.2.2. Study Phase and Period

Safety assessments and events will be classified according to the time of occurrence relative to the study intervention period.

Table 13 Study Phase Definitions

Study Intervention Phase	Definition
Pre-Treatment	For Assessments – Date ¹ ≤ Study Treatment Start Date For Events – Date ¹ < Study Treatment Start Date
On-Treatment	For Assessments – Study Treatment Start Date < Date ¹ < Last Treatment Stop Date + 7 days For Events – Study Treatment Start Date ≤ Date ¹ < Last Treatment Stop Date + 7 days
Post-Treatment	Date ¹ ≥ Last Treatment Stop Date + 7 days

¹ Date is the start date of the assessment/event.

Table 14 Study Period Definitions

Study Intervention Period	Definition
GSK3228836 Treatment Period	For Assessments – All Analysis Timepoints within : WK 1 DAY 1 to a day prior PEGIFN ELIGIBILITY WK 1 DAY 1* For Events – Study Treatment Start Date ≤ Date ¹ < GSK836 Last Treatment Date + 7 days
PegIFN Eligibility Period	For Assessments – All Analysis Timepoints within : 1) PEGIFN ELIGIBILITY WK 1 DAY 1 to a day prior PEGIFN DOSING WK 1 DAY 1* and 2) PEGIFN ASSESSMENT WK 14 to a day prior OT-W1 OT-DAY 1*

Study Intervention Period	Definition
	For Events – $GSK836 \text{ Last Treatment Date} + 7 \text{ days} \leq \text{Date}^1 < \text{PegIFN Treatment Start Date}$ *if subject withdrew or never received PegIFN dosing before PegIFN Dosing Visit then end of period would be 'Last PegIFN Assessment Week Stop Date + 7 days'
PegIFN Treatment Period	For Assessments – All Analysis Timepoints within : PEGIFN DOSING WK 1 DAY 1 to a day prior OT-W1 OT-DAY 1* For Events – $\text{PegIFN Treatment Start Date} \leq \text{Date}^1 < \text{PegIFN Treatment Stop Date} + 7 \text{ days}$
Follow-up Period	For Assessments – All Analysis Timepoints within : OT-W1 OT-DAY 1* onwards For Events – If subject never received PegIFN dosing and did not discontinue on-treatment - $\text{Date}1 \geq \text{Last PegIFN Assessment Week Stop Date} + 7 \text{ days}$ Else $\text{Date}1 \geq \text{Last Treatment Stop Date} + 7 \text{ days}$

¹ Date is the start date of the assessment/event.

* If a subject withdrew early or skipped period(s), consider start of next period analysis timepoint. If analysis timepoint is not collected, use corresponding planned start visit day in Section 6.2.8.

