4. STUDY DESIGN

4.1. Overall Design

This is a Phase IIb, multi-centre, randomised, open-label study to assess the efficacy and safety of sequential treatment with GSK3228836 (300 mg/week for 12 or 24 weeks) followed by PegIFN (180 mcg/week for up to 24 weeks) in participants with CHB on stable NA therapy. During the GSK3228836 treatment period, a 300 mg loading dose will be administered on Day 4 and Day 11. Participants will continue their NA therapy for the duration of the study.

Participants will be randomised (1:1) into one of two parallel treatment arms.

1. 300 mg GSK3228836 once/week for 24 weeks (plus loading dose on Day 4 and 11) followed by PegIFN (180 mcg/week for up to 24 weeks). Participants will be followed up for an additional 24 weeks (off-treatment phase) once PegIFN treatment is complete.

2. 300 mg GSK3228836 once/week for 12 weeks (plus loading dose on Day 4 and 11) followed by PegIFN (180 mcg/week for up to 24 weeks). Participants will be followed up for an additional 36 weeks (off-treatment phase) once PegIFN treatment is complete.

The planned duration of GSK3228836 is 24 weeks and 12 weeks in Treatment Arm 1 and 2 respectively. If a participant prematurely discontinues GSK3228836 treatment the participant is encouraged to complete the SoA as per the planned GSK3228836 dosing period. At the end of the planned GSK3228836 dosing period, participants will be re-assessed for eligibility to start PegIFN treatment based on the label.

1. Participants immediately eligible for PegIFN will begin treatment
2. Participants who are not considered eligible will be re-assessed for eligibility and may delay start of PegIFN treatment for up to 12 weeks.
3. Participants who fail to meet PegIFN eligibility criteria by PegIFN Eligibility Week 13 (i.e. can no longer receive at least 12 weeks of PegIFN treatment) will not receive treatment with PegIFN.

Note: all participants are expected to end PegIFN treatment at the same time, regardless of when they start therapy (Treatment Group 1: all participants should complete treatment by Week 48; Treatment Group 2: Week 36).

As such, the planned treatment duration with PegIFN for participants on study 209348 may vary from a minimum of 12 weeks to a maximum of 24 weeks.

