Tenofovir, entecavir, and other NAs circulated in the blood stream with little binding to serum proteins [Bristol-Myers Squibb, 2018; Gilead 2018]. Tenofovir, entecavir, lamivudine, adefovir and telbivudine are predominantly renally eliminated from systemic circulation [Epivir, 2002; Kearney, 2004; Hepsera, 2012; Tyzeka, 2013; Entecavir, 2015; Bristol-Myers Squibb, 2018; Gilead, 2018]. These 5 drugs undergo a combination of glomerular filtration and tubular secretion, which have been reported to be mediated by one or more of the following transporters: the organic anion transporter (OAT) 1, OAT3, the organic cation transporter (OCT) 1, and OCT2 [Cihlar, 2001; Cihlar, 2004; Servais, 2006; Uwai, 2007; Minuesa, 2009; Yanxiao, 2011; Xu, 2013]. It has been shown that 2'-MOE ASO is neither a substrate nor an inhibitor of OAT1, OAT3, OCT1 and OCT2

[Yu, 2016; Shemesh, 2017]. Therefore, although GSK3228836 was shown to be extensively distributed into the kidney in non-clinical studies, it is unlikely to interact with tenofovir, entecavir, lamivudine, adefovir, telbivudine, or other NAs.

In Cohorts 1-3 of the ISIS 505358-CS3 study, treatment naïve participants were started on tenofovir after treatment ended; in Cohort 4, where participants were NA-experienced, the majority of participants were on entecavir. Clinical data from this study suggest that co-administration of GSK3228836 is unlikely to impact efficacy and safety profiles. In Cohorts 1 to 3 in ISIS 505358-CS3 study, GSK3228836 was administered alone for 4 weeks, and then tenofovir dosing was started on Study Day 29 (7 days after the last dosing of GSK3228836). Given the long plasma and tissue half-life of GSK3228836 (approximately 3 weeks), there is a period of at least several weeks during which there was a substantial presence of both drugs in the plasma, liver and other tissues. Potent reduction of HBV DNA was observed following initiation of tenofovir in all participants. There were no obvious differences in tenofovir potency and efficacy in participants who received 150 mg of GSK3228836 (Cohort 1), 300 mg of GSK3228836 (Cohorts 2 and 3), and placebo (no GSK3228836). There were no adverse event or clinical laboratory results that may indicate a change in tenofovir safety profile due to drug-drug interaction with GSK3228836.

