4.5.2. Adverse Events

All AE summaries will be based on treatment emergent events unless otherwise specified. An adverse event (AE) is considered treatment emergent if the AE onset date is on or after treatment start date. If AE start date is completely missing and the end date is on or after the treatment start date, the AE will be assumed to be treatment emergent. AEs with onset date on or after start date of treatment with GSK3228836 will be classified as occurring during the GSK3228836 treatment period, and AEs with onset date on or after start date of treatment with PegIFN will be classified as occurring during the PegIFN treatment period. AEs starting after end of GSK3228836 treatment period and prior to PegIFN treatment start will be considered as AEs occurring during PegIFN eligibility period.

Adverse events will be coded using the latest version of Medical Dictionary for Regulatory Authorities (MedDRA) coding dictionary, to give a preferred term and a system organ class. These preferred terms and system organ classes will be used when summarizing the data.

The severity of AEs and SAEs will be determined by the investigator according to the 'Division of Acquired Immune Deficiency Syndrome (DAIDS) Table for Grading the Severity of Adult and Pediatric Adverse Events (2017)', unless specified otherwise in the protocol. For AEs by maximum determined grade summary tables, for AEs occurred more than once, the most severe intensity will be included in summaries. Relationship to study treatment, as indicated by the investigator, is classified as not related or related to GSK322836, PegIFN, or both. Adverse events with a missing relationship to study treatment will be regarded as related to the ongoing study treatment or the last study treatment if no treatment is received at the time of AEs.

The following AE summaries will be presented overall and by treatment arm:

1. AEs overview: summarize the number and percentage of participants with any adverse event, AEs related to study treatment, AEs leading to permanent discontinuation of study treatment, withdrawal from the study, any serious adverse events (SAE), SAEs related to study treatment, fatal SAEs and fatal SAEs related to study treatment.
2. All AEs by system organ class (SOC) and preferred term (PT)
3. All AEs by SOC and PT and maximum grade
4. All drug-related AEs by SOC and PT
5. All drug-related AEs by SOC and PT and maximum grade
6. Serious AEs (SAEs) by SOC and PT

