7. Serious AEs (SAEs) by SOC and PT and maximum grade
8. Serious Adverse Events by system organ class and preferred term (number of participants and occurrences)
9. AEs leading to withdrawal from the study by SOC and PT
10. AEs leading to withdrawal from the study by SOC and PT and maximum grade
11. AEs leading to permanent discontinuation of study treatment by SOC and PT
12. AEs leading to permanent discontinuation of study treatment by SOC and PT and maximum grade
13. Serious fatal and non-fatal drug/related AEs by SOC and PT
14. AEs by overall frequency
15. Non-serious AEs by SOC and PT (number of participants and occurrences)
16. Non-Serious drug-related adverse events by overall frequency

The above listed summaries will also be presented separately for events occurring during treatment with GSK3228836 and PegIFN, overall and by treatment arm within each treatment period. Drug-related AEs will be summarised for the two treatment periods as follows:

1. Summary of GSK3228836 drug-related adverse events by system organ class and preferred term
2. Summary of GSK3228836 drug-related adverse events by system organ class and preferred term and maximum grade
3. Summary of PegIFN drug-related adverse events by system organ class and preferred term
4. Summary of PegIFN drug-related adverse events by system organ class and preferred term and maximum grade

Number of participants with AEs will be summarized if it is not specified otherwise.

In summary tables where AEs are presented by SOC, PT, and maximum grade, SOC's will be sorted in descending order of the total incidence then alphabetically, PT's will be sorted in descending order of the total incidence then alphabetically within the SOC.

For completely missing or partial missing AE start date or end date, imputation rules will be applied following rules stated in the Output and Programming Specifications (OPS).

Deaths will be listed including primary cause of death.

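### SAP Table 14 puts the AEs and labs of early GSK3228836 stoppers on different period clocks, and SAP 4.5.2 gives the PegIFN period no end

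*SAP*

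**What the plan says.** SAP 6.2.2, Table 14, defines each study period twice, once for assessments and once for events.

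- **GSK3228836 period, events:** from the first dose up to, but not including, "GSK836 Last Treatment Date + 7 days".
- **GSK3228836 period, assessments:** the timepoints from "WK 1 DAY 1 to a day prior PEGIFN ELIGIBILITY WK 1 DAY 1". A footnote adds: "If a subject withdrew early or skipped period(s), consider start of next period analysis timepoint". If that timepoint was not collected, the planned day in SAP 6.2.8 is used.
- **Eligibility period, events:** from the last GSK3228836 dose + 7 days to the PegIFN start. If PegIFN is never given, it runs to the last PegIFN assessment week + 7 days.
- **Follow-up, events:** for a participant who never received PegIFN and did not discontinue on treatment, it starts at the last PegIFN assessment week + 7 days. For everyone else it starts at the last treatment + 7 days.
- **PegIFN period, events:** from the first PegIFN dose to the last PegIFN dose + 7 days.

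SAP 4.5.2 gives its own rules, with start dates only. For the second drug it states: "AEs with onset date on or after start date of treatment with PegIFN will be classified as occurring during the PegIFN treatment period". Its rule for GSK3228836 has the same form and likewise names no end. It then plans for the AE summaries to be "presented separately for events occurring during treatment with GSK3228836 and PegIFN, overall and by treatment arm within each treatment period". No by-period AE table is named for Eligibility or Follow-up. SAP 4.5.3.1 plans lab summaries for the same two drug periods.

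Protocol 4.1 states: "If a participant prematurely discontinues GSK3228836 treatment the participant is encouraged to complete the SoA as per the planned GSK3228836 dosing period".

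**The concern.** By-period AE and lab tables under the same label should cover the same calendar time. For an early stopper who keeps attending the planned GSK3228836 visits, they do not. A low platelet value can be counted in the GSK3228836 lab tables while the AE that reports it, with onset on the same date, is assigned to Eligibility. Since only the GSK3228836 and PegIFN periods are tabulated, that AE then appears in neither by-period AE table.

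Participants who stop for liver, platelet, renal or complement findings are among those affected, and they are the people whose AEs and labs a safety reader will try to match up. Two programmers could also build different PegIFN tables from the same SAP, one following 4.5.2 and one following Table 14.

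**Working it through.** The plan states no figure here to reproduce, so the check is date arithmetic on its own rules.

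**Inputs**
- Planned last GSK3228836 dose: day 162 (Arm 1) or day 78 (Arm 2), from the protocol's Schedule of Activities, Tables 2 and 3.
- PegIFN Eligibility Week 1 (SAP 6.2.8, Table 19): Arm 1, 1 + 7 × (23 + 1) = day 169; Arm 2, 1 + 7 × (11 + 1) = day 85.
- PegIFN Week 24: Arm 1, 1 + 7 × (23 + 24) = day 330; Arm 2, 1 + 7 × (11 + 24) = day 246.
- Final scheduled visit: day 498 in both arms (SAP Table 19).

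**1. Gap between the AE and lab boundaries.** Let L be the day of the last GSK3228836 dose and E the day of Eligibility Week 1. AEs leave the period from day L + 7, and labs stay through day E − 1, so the gap is E − (L + 7) days.

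| Arm | Last dose (day) | AEs out from day | Labs in through day | Gap (days) |
|---|---|---|---|---|
| 1 | 162 (on schedule) | 169 | 168 | 0 |
| 1 | 141 | 148 | 168 | 21 |
| 1 | 85 | 92 | 168 | 77 |
| 1 | 36 | 43 | 168 | 126 |
| 1 | 1 (maximum) | 8 | 168 | 161 |
| 2 | 78 (on schedule) | 85 | 84 | 0 |
| 2 | 57 | 64 | 84 | 21 |
| 2 | 29 | 36 | 84 | 49 |
| 2 | 1 (maximum) | 8 | 84 | 77 |

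**2. Overlap of Eligibility and Follow-up.** Take the Arm 1 participant with L = 36 who never receives PegIFN and attends through PegIFN assessment Week 24 (day 330). The Eligibility event period runs from day 43 to before day 330 + 7 = 337. The participant did discontinue on treatment, so Follow-up takes its default branch and also starts at day 43. Days 43 to 336, that is 337 − 43 = 294 days, satisfy both definitions.

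**3. Overlap of the two drug periods.** With the ±3-day visit windows, a last GSK3228836 dose on day 165 and a first PegIFN dose on day 166 give 165 + 7 − 166 = 6 days in both drug periods.

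**4. Length of the PegIFN period.**
- Table 14: Arm 1, days 169 to 336; Arm 2, days 85 to 252. Each is 168 days, or 24 weeks.
- 4.5.2 read literally: to the end of study, nominally 24 + 24 = 48 weeks in Arm 1 and 24 + 36 = 60 weeks in Arm 2, a ratio of 60/48 = 1.25. Counted to the day-498 visit, this adds 498 − 337 + 1 = 162 days in Arm 1 and 498 − 253 + 1 = 246 days in Arm 2.

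**The case against.** The strongest reply is that nothing is lost from the safety analysis. Treatment emergence in SAP 4.5.2 and 6.2.6 has no end date, so every AE in question stays in the overall by-arm tables. The toxicities that force early stopping are the AESIs of SAP 4.5.2.1, which are summarised without a period restriction. SAP 4.5.3.1 adds individual profiles for anyone meeting a hold or stopping criterion. An AE that triggers stopping will normally start before the last dose + 7 days and so remains in the GSK3228836 period. All of this stands. A reader might infer that the plan understates GSK3228836 toxicity, but the documents do not support that: only later onsets move, only in the by-period tables, and no size is shown.

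Second, protocol 4.1 only encourages early stoppers to stay on schedule, and protocol 7.1.1 sends liver stoppers to follow-up visits after monitoring. For those who withdraw or skip periods, the Table 14 footnote moves the lab boundary. This also stands and limits the AE/lab split to early stoppers who stay on the planned visits.

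Third, a reader might infer that 4.5.2 contradicts Table 14 on the end of the GSK3228836 period. It does not. It mentions such an end without defining it, which is compatible with Table 14. Only the PegIFN end conflicts, and the 48 versus 60 weeks arises only if Table 14 is set aside.

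Fourth, one weekly dosing interval after the last dose is a defensible on-treatment window in itself. A reader might cite the half-life of about 3 weeks (protocol 4.3), under which 2^(−7/21) = 79% of the drug remains at 7 days. That applies equally to completers, whose GSK3228836 period also ends there, so it does not measure this defect. What the reply leaves unanswered is the use of different boundaries for events and assessments under one period name.

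**Conclusion.** The point holds as a defect in the by-period safety rules, worth correcting but not a threat to the overall safety reporting. Three things are confirmed from the text:

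- Events and assessments leave the GSK3228836 period on different clocks. The gap is zero for on-schedule completers, 126 days for an Arm 1 last dose on day 36, and at most 161 days (Arm 1) or 77 days (Arm 2).
- The Eligibility and Follow-up event definitions overlap for an early stopper who never receives PegIFN.
- The PegIFN period has no end in 4.5.2 but ends at the last dose + 7 days in Table 14: about 48 and 60 weeks against about 24 in each arm.

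The first item assumes that the participant stays on the planned visits. The second assumes that stopping GSK3228836 early counts as discontinuing on treatment, which is the natural reading of Table 14. The documents give no number of early stoppers, so the count of displaced AEs cannot be computed.

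**What to change.** 1. In Table 14, apply the existing assessment boundary to events. For every participant the GSK3228836 period then ends the day before PegIFN Eligibility Week 1 (the planned day in SAP 6.2.8 if not collected), or the day before the first PegIFN dose if that is earlier, whether or not PegIFN is later started. Keep the existing footnote for those who withdraw or skip periods, and start the Eligibility event period where the GSK3228836 period ends.
2. Amend SAP 4.5.2 to use Table 14's PegIFN end for AEs, the last PegIFN dose + 7 days, and refer to Table 14 for the other boundaries.
3. Revise the default branch of the Follow-up definition so that no event can fall in both Eligibility and Follow-up.
4. Add Eligibility and Follow-up columns to the by-period AE tables, so that every treatment-emergent AE appears in exactly one period.

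Using the same GSK3228836 boundary whether or not PegIFN is started matters. A rule that ran to the first PegIFN dose for starters but stopped at Eligibility Week 1 for never-starters would add up to 12 weeks of eligibility delay for one group only.

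The cost is SAP wording, reprogramming of one period flag and two extra columns, with no new data. Slightly more AEs will be counted in the GSK3228836 period.
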